Once caregivers verbally understand and agree to these responsibilities they will be sent the surrogate consent form for the PWD, the self-certification of surrogate decision maker form, and their own consent form via a Qualtrics link. If the investigator's evaluation is that the PWD can provide consent, the PWD will be asked to complete their own consent form via Qualtrics. Once all forms are completed, a link to the first questionnaire administration will be sent for the caregiver. Identical Qualtrics questionnaires will be sent via email to caregivers in both research conditions at baseline, 3 months, and 6 months. The three sets of questionnaires will be identical, except: (a) the baseline questionnaire will also include a contact information form and "Information about person receiving care"; and (b) the 3-month and 6-month questionnaires will also include questions regarding the usefulness of Presence Care in their homes.

Randomization:

300 caregivers will be randomly assigned to the "active in-home technology" condition of Presence Care and the remaining 100 caregivers will be assigned to the "waiting control" condition. Randomization of participants in each group will be determined by People Power employees after the consent process.

Outcome Measures:

All caregivers—regardless of randomized study condition—complete questionnaires on three separate occasions during this study: baseline, 3-months, 6-months. The four outcome measures

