Developing and Evaluating In-Home Supportive Technology for Dementia Caregivers, Phase
IIB
R44AG059458-03
April 14, 2022

Statistical Analysis Plan

Primary Outcomes

All caregivers—regardless of randomized study condition—complete questionnaires on three separate occasions during this study: baseline, 3-months, 6-months. The four outcome measures include changes over the 6-month study period for the following scales: Zarit Burden Interview-Short Form, a questionnaire measuring caregiver burden (Zarit, Reever, & Bach-Peterson, 1980). 12 items are rated on 0-4 scale. Range: 0-48. No subscales. Higher scores represent worse outcomes; Center for Epidemiological Studies Depression Scale (CES-D), a questionnaire measuring depression (Radloff, 1977). 20 items are rated on a 0-3 scale and summed (range = 0-60). There are no subscales. Higher scores represent worse outcomes. The clinical cut-off is usually set at a score of 16; Beck Anxiety Inventory (BAI), a questionnaire measuring anxiety (Beck, Epstein, Brown, & Steer, 1988). 20 items are rated on a 0-3 scale and summed (range= 0-60). Higher scores indicate worse outcomes. There are no subscales. A score greater than 36 is considered to be clinically significant.; and Satisfaction with Life Scale, a questionnaire measuring overall life satisfaction and well-being (Diener, Emmons, Larsen, & Griffin, 1985). 5 items scored on a 1-7 scale and summed (Range = 5-35). Lower scores indicate worse outcomes. A score of 20 is considered neutral with higher scores considered increasingly more satisfied and lower scores considered increasingly more dissatisfied.

Statistical Methods

Design: Caregivers will be randomized into two groups: Active In-Home Technology System and Waiting Control. Subjects will be randomized 3:1. Randomization of participants in each group will be determined by People Power employees. With a total N of 400 caregivers in two conditions and measures repeated three times, a comparison between groups using ANOVA will have .80 power to detect a medium effect size at $p=.05$.

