Analysis: Descriptive statistics will be used to summarize all the clinical characteristics and demographic outcomes. These will be summarized overall, by treatment group, by assessment time, and by treatment group and time. Continuous variables will be summarized using means, standard deviations, and ranges. Categorical data will be summarized by number and percent. To evaluate the treatment effects, we will use repeated measures ANOVAs. The other predictors will be treatment group, and time (baseline, 3-months, and 6-months for caregiver outcomes). To evaluate treatment effects, an interaction term between treatment group and time will be included to examine treatment group-related differences in the assessments for each outcome. Each significant interaction will be followed up with paired t-tests to examine treatment differences at each set of time points. Although this study involves 4 outcomes, we do not plan formal multiple comparison adjustments if the results fit a coherent pattern that is consistent with the context of

similar studies. In this case, each result will reinforce the other, rather than detracting from one another, as required by formal multiple comparisons adjustments such as Bonferroni. Conversely, if only one or a very few measures reach statistical significance and their directions and/or magnitudes do not coherently fit with our a prior expectations, then we will note that the result(s) with $p < 0.05$ lack plausibility and could be due to chance, despite meeting the conventional cutoff for statistical significance.

Missing Data: If subjects either cannot or refuse to complete surveys we will use a sensitivity analysis approach in dealing with these missing data by performing analysis with 2 versions of scores: 1) with missing item interpolated using mean replacement by group, and 2) only using responses with 0% missing data. If the results differ for the two approaches, then we will report on the differences.

REFERENCES

Bedard, M., D.W. Molloy, L. Squire, S. Dubois, J.A. Lever, and M. O'Donnell, The Zarit Burden Interview: a new short version and screening version. *Gerontologist*, 2001. 41(5): p. 652-7.

Radloff, L.S., The CES-D scale: A self-report depression scale for research in the general population. *Applied Psychological Measurement*, 1977. 1: p. 385-401.

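### The 2-df group-by-time test does not isolate the between-arm difference in 6-month change, and the SAP names no estimate or confidence interval for it

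*SAP*

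**What the plan says.** The SAP, under Primary Outcomes, states: "The four outcome measures include changes over the 6-month study period for the following scales". The scales are completed at baseline, 3 months and 6 months.

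Under Statistical Methods, Analysis, the model is given as "To evaluate the treatment effects, we will use repeated measures ANOVAs". Its predictors are group and time, with baseline as the first of three time levels. The treatment effect is carried by one term: "an interaction term between treatment group and time will be included to examine treatment group-related differences in the assessments for each outcome". Paired t-tests follow, but only where that interaction is significant. No baseline covariate, between-arm contrast or confidence interval is named.

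Under Design, the SAP says "Subjects will be randomized 3:1", and the Protocol's Randomization section gives 300 active and 100 waiting control. The power statement reads "With a total N of 400 caregivers in two conditions and measures repeated three times", then "a comparison between groups using ANOVA will have .80 power" "to detect a medium effect size" at the .05 level. It does not say which ANOVA term it refers to. It gives no numeric effect size, SD, within-person correlation or dropout rate.

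**The concern.** The outcome and the test do not line up. The outcome is a change over 6 months, so the natural result is one number per scale: how much more the active arm changed than control by month 6. The planned test asks instead whether the two three-point profiles differ in any way. Four things follow.

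- A significant result need not mean a 6-month benefit; a transient month-3 difference is enough.
- The F test has no sign. The SAP's multiplicity rule relies on whether the directions and magnitudes across the four outcomes are coherent, and the treatment test supplies neither.
- The paired t-tests do not fill the gap. They compare times within the same people and cannot estimate a difference between two independent arms. Repairing them alone would leave the gate in place: an effect that misses the 2-df test would still not be followed up.
- Baseline is collected from everyone but used only as a level of the response. In some plausible settings that costs power.

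**Working it through.** **Inputs from the documents.** 300 active, 100 control, three time points, alpha .05.

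**Assumptions, because the documents give none.** SD 1 in both arms, two-sided test, no dropout, 6-month effect d of 0.3 or 0.5 SD, correlation r between waves of .3 to .8. Correlations are either equal across waves or decay as a power of r per 3-month interval. Effect shapes: linear (half by month 3), step (full at both visits), late (month 6 only), early (month 3 only).

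**1. The plan's own figure.** Reading a medium effect as d = 0.5 (an assumption), a plain two-group comparison has noncentrality (300 × 100/400) × 0.5² = 75 × 0.25 = 18.75, which gives power .991, not .80. With these arm sizes, .80 corresponds to d = 0.32. The stated .80 may be meant as a minimum, but it identifies neither the test nor the effect size. It therefore cannot show that the interaction, or any 6-month contrast, is adequately powered.

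**2. What the planned term tests.** Degrees of freedom are (2 − 1)(3 − 1) = 2. With baseline as a time level, the null hypothesis is that the between-arm differences in change to month 3 and to month 6 are both zero.

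**3. Formulas, equal correlations.** Let d_t be the between-arm difference at each wave.
- Planned interaction: λ = 75 × Σ(d_t − mean d)² / (1 − r), F on 2 and 796 df.
- 6-month score adjusted for baseline: λ = 75 × d² / (1 − r²), F on 1 and 397 df.

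**4. A difference at month 3 only, 0.3 SD.** Differences are 0, 0.3, 0, so the sum of squares is 0.06. At r = .5, λ = 75 × 0.06/.5 = 9.0 and power is .77. At r = .7, λ = 15.0 and power is .94. The true 6-month difference is zero, so a 6-month contrast rejects 5% of the time.

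**5. Linear effect, 0.3 SD at month 6.** Differences are 0, 0.15, 0.3, so the sum of squares is 0.045.

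| r | λ planned | power planned | λ adjusted | power adjusted |
|---|---|---|---|---|
| .5 | 75 × 0.045/.5 = 6.75 | .64 | 6.75/.75 = 9.00 | .85 |
| .6 | 75 × 0.045/.4 = 8.44 | .74 | 6.75/.64 = 10.55 | .90 |
| .7 | 75 × 0.045/.3 = 11.25 | .86 | 6.75/.51 = 13.24 | .95 |

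**6. Linear effect, 0.5 SD.** At r = .3: .915 planned, .995 adjusted, a loss of 8 points. At r = .5: .979 against .999. At r = .7 both are about 1.

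**7. Where the planned test ties or wins, 0.3 SD.**
- Step or late effect, correlation decaying at .8 per interval: .96 planned (simulated split-plot F) against .92 adjusted.
- The same shapes at .7 per interval: about .86 against .85.
- The same shapes, equal correlation .8: .993 against .991.

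**8. Unequal variances.** With 3:1 arms and no true effect, the pooled interaction test has simulated type I error of about .09 if the control SD is 1.25 times the active SD, and about .02 if reversed (equal correlations .5 and .7). The 1.25 ratio is an assumption; it shows only that the pooled error term is sensitive at this allocation.

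**The case against.** The interaction is a valid test of differential change in a randomized trial. It includes the baseline-to-month-6 contrast, so a reader who infers that the plan ignores the 6-month change goes too far. Changes over the study period can also fairly be read as the whole trajectory. That stands: the fault is failure to isolate the contrast, not failure to include it.

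A reader might also infer that the plan is simply underpowered. The documents do not support this. They give no correlation, effect shape or numeric effect. At 0.5 SD the planned test keeps at least .91 power in the settings tried, and in some step and late patterns it beats the adjusted 6-month test. Nor can the loss be expressed as a fixed percentage of extra caregivers. That calculation compares baseline adjustment with an unadjusted change score, which is not the planned test.

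Finally, the SAP will tabulate means and SDs by group and time, so crude differences and their direction will be visible, and it does intend some follow-up of treatment differences. But a descriptive table is not a specified estimate with a confidence interval, and the follow-up named is within-person and conditional on the gate.

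**Conclusion.** The concern holds, as a gap in what is estimated. From the text alone, with no assumptions: the treatment test is a 2-df omnibus term, baseline is not a covariate, all follow-up depends on that test, and no between-arm 6-month difference with a confidence interval is specified. The plan as written can therefore finish without a formal answer to how much better, or worse, the active arm is at 6 months.

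The practical size is clearest for a month-3-only difference of 0.3 SD: the planned test is significant about 77% to 94% of the time at equal correlations of .5 to .7, with nothing present at month 6. The power loss is real in some settings (up to about 21 points for a linear 0.3 SD effect at correlation .5 to .7), small at 0.5 SD, and absent or reversed in others. It supports the change but is not the main reason for it. The change should be made; the trial is not invalid without it.

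**What to change.** Replace the treatment-effect sentences under Statistical Methods, Analysis, with:

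> For each outcome, follow-up scores at 3 and 6 months will be analysed in a longitudinal mixed model with group, time, group-by-time and baseline score by time, with unstructured covariance and variance estimates that do not assume equal variances in the two arms. The primary test is the active-minus-control difference at 6 months with its 95% CI; the 3-month difference is secondary and the interaction test is descriptive.

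Restate the power sentence for that contrast, with a numeric effect size, SD, correlation and dropout rate.

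Cost: SAP wording only, with no new data or participants. Downside: some power is given up relative to the 2-df test if the whole effect is present by month 3, or appears only at month 6, and correlations decay over time (for example .92 against .96 at .8 per interval) or are high (about .8, where the difference is negligible).

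### The follow-up paired t-tests cannot show the treatment differences they are meant to show, and no between-arm difference with a confidence interval is planned

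*SAP*

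**What the plan says.** The SAP (Statistical Methods, Design) describes two independent arms: "Caregivers will be randomized into two groups: Active In-Home Technology System and Waiting Control. Subjects will be randomized 3:1". The Protocol (Randomization) puts 300 caregivers in the active condition, and "the remaining 100 caregivers will be assigned to the" waiting control. Neither document describes matching across arms.

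The SAP (Primary Outcomes) sets the target: "The four outcome measures include changes over the 6-month study period for the following scales". Under Analysis, treatment effects are tested by repeated measures ANOVA, in which "an interaction term between treatment group and time will be included to examine treatment group-related differences in the assessments for each outcome". The follow-up step is: "Each significant interaction will be followed up with paired t-tests to examine treatment differences at each set of time points".

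The descriptive summaries do cover arm and visit: "These will be summarized overall, by treatment group, by assessment time, and by treatment group and time", and "Continuous variables will be summarized using means, standard deviations, and ranges". No between-arm difference and no confidence interval appears in either document.

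The SAP makes no formal multiplicity adjustment over the four scales if the results are coherent. A result counts against coherence when "their directions and/or magnitudes do not coherently fit with our a prior expectations".

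**The concern.** The follow-up is the only step that could say at which visit the arms differ and by how much, and the test chosen for it does not compare the arms. Whether a within-arm change reaches significance depends on the change both arms share and on the arm's size (300 against 100), as well as on any treatment effect. The same true treatment difference can therefore give quite different patterns of paired-test results.

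Two things are at stake. The report would carry no prespecified effect size or interval for any of the four outcomes. The coherence rule would also have to judge direction and magnitude with no between-arm contrast named for it: an omnibus interaction has no direction, and a within-arm change is not a treatment effect.

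**Working it through.** **Which pairs exist.** Different caregivers are in each arm and none are matched. The only paired observations are one caregiver's scores at two visits, so a paired t-test addresses change over time within an arm or pooled over arms.

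**What the interaction delivers.** With 2 arms and 3 visits, its numerator df are (2−1)×(3−1) = 2 and its error df are (400−2)×2 = 796. It is a between-arm test, but it does not identify a visit, a sign or a size.

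**The plan's own figure.** The SAP gives none on this point. Its power of .80 for a medium effect is not reproduced if medium means d = 0.5: at 300:100 the power is 0.991, and 0.80 corresponds to d of about 0.32. That is a separate matter and does not enter below.

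**Effect of arm size alone.** Suppose both arms change by the same amount. Let dz be that change divided by the SD of change, which is √(2(1−ρ)) in score-SD units. The paired test's noncentrality is dz×√n. At dz = 0.2 this is 0.2×√300 = 3.46 in the active arm and 0.2×√100 = 2.00 in control, giving power of 0.932 and 0.508. The chance that only the active arm is significant is 0.932×(1−0.508) = 0.458, with no true difference. At dz = 0.10, 0.15 and 0.30 it is 0.339, 0.502 and 0.156. These figures ignore the requirement of a significant interaction.

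**With the interaction required first.** The documents give no correlation, shared change or effect pattern, so all of these are assumed: 300/100, complete data, compound symmetry, ρ = 0.5 and 0.6, units of score SD, two-sided 0.05, and an improvement shared by both arms that builds linearly to 0–0.4 SD at 6 months. There were 200,000 simulated trials per scenario. *Active only* means that the baseline-to-6-month paired test is significant in the active arm and not in control. Ranges run over the two values of ρ.

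If the arms differ at no visit, a significant interaction together with *active only* occurs in 0.4–2.5% of all trials, so the interaction test does limit false claims.

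The rows for shared improvement and for the between-arm test give percentages of trials with a significant interaction:

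| Shared improvement by 6 months (SD) | Effect 0.3 at 3 months, 0 at 6: active only | Effect 0.3 at 3 months, 0.15 at 6: active only | Gradual effect, 0.3 at 6 months: active only | Same gradual effect: both arms significant, same direction |
|---|---|---|---|---|
| 0 | 5 | 74–81 | 96–97 | 0.1 |
| 0.1 | 34–39 | 85–87 | 94–97 | 3–6 |
| 0.15 | 50–51 | 69–76 | 79–89 | 11–21 |
| 0.2 | 39–46 | 48–60 | 53–71 | 29–47 |
| 0.3 | 9–17 | 12–23 | 12–24 | 76–88 |
| 0.4 | 1–3 | 1–4 | 1–4 | 97–99 |
| Between-arm test of the same change, any shared improvement | 6 | 37–40 | 98–99 | (as left) |
| Interaction significant (% of all trials) | 77–86 | 64–74 | 64–74 | (as left) |

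Down each column the true treatment effect is fixed. The between-arm test does not move, because shared change cancels; the paired pattern does. With no shared change, the paired tests separate true 6-month differences of 0, 0.15 and 0.3 SD (5%, 74–81%, 96–97%). At 0.4 SD they give 1–4% for all three.

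**Precision of the missing interval.** Half-width = 1.966×k×√(1/300+1/100), and the square root is 0.1155. Adjusted for baseline, k = √(1−ρ²), giving 0.197 (ρ = 0.5) and 0.182 (ρ = 0.6). For the difference in change, k = √(2(1−ρ)), giving 0.227 and 0.203.

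**The case against.** The strongest defence is that the SAP gives the job of evaluating treatment effects to the interaction, which is valid, and nowhere says that significance in one arm but not the other will be read as a treatment effect. That is true. But the SAP does tell the analyst to use the paired tests for treatment differences, and it offers no other follow-up.

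The table covers only one of the three visit pairs. This matters most in its first scenario. Where *active only* appears from baseline to 6 months, the active arm's 3-to-6-month test also shows a significant reversal in 95–99.8% of cases at shared improvement of 0.1–0.2 SD, so a reader of all three pairs would usually see the early gain and its loss. The 34–51% in that column should be discounted accordingly. This does not rescue the other two scenarios: in the waning one the reversal is seen in only about 16% at shared improvement of 0.2 SD, and in the gradual one there is none to see.

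The assumed shared change is always improvement, and the documents give no sign. With shared worsening of 0.3 SD and the gradual effect, the dominant pattern becomes significance in control only (93–95%). The pattern is different, but it depends on shared change in the same way.

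The planned means by arm and visit let a reader subtract one arm from the other. For the gradual effect at shared improvement of 0.2 SD, trials with both arms significant have mean changes of about 0.52–0.54 (active) and 0.23–0.24 (control). Size and direction are therefore visible, and the gap is narrower: no named contrast and no interval.

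Finally, *paired* may be a slip for *pairwise*. The wording would then still need correcting, and an estimate with a CI would still be missing.

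**Conclusion.** The concern holds and should be fixed. That a paired test cannot compare two independent arms, and that neither document specifies a between-arm contrast or a CI, follow from the text and need no assumptions. The main test is sound and no inflation of false-positive claims is alleged.

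The size of the problem is conditional. Under the stated assumptions, and with a fixed gradual effect of 0.3 SD at 6 months, the active-only pattern runs from 96–97% down to 1–4% as shared improvement goes from 0 to 0.4 SD, while the between-arm contrast stays at 98–99%. Different correlations, dropout or shared worsening would change these figures, but not the dependence on shared change and arm size.

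**What to change.** Replace the paired t-tests in the SAP's Analysis paragraph with between-arm contrasts:

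- For each of the four scales, prespecify the active-minus-control difference at 6 months and at 3 months. State whether it is adjusted for that scale's baseline score or is a contrast of change from baseline taken from the model.
- Report each with a 95% CI, whether or not the interaction is significant.
- State that the coherence rule takes direction and magnitude from these estimates.
- Keep the interaction test as planned, and report within-arm changes descriptively only.

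The cost is SAP wording and eight contrasts (two for each of four scales). The baseline, 3-month and 6-month scores are already collected. At the planned size, with complete data and ρ of 0.5–0.6, the interval would have a half-width of 0.18–0.20 SD adjusted for baseline, or 0.20–0.23 SD for the difference in change.

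### Four unranked primary outcomes are each read at p < .05, and multiplicity is settled only after the results are seen, by a coherence criterion that the SAP does not define

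*SAP*

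**What the plan says.** SAP, Primary Outcomes, puts four scales (caregiver burden, depression, anxiety, life satisfaction) under one heading with no order and no single primary: "The four outcome measures include changes over the 6-month study period for the following scales".

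SAP, Statistical Methods, Analysis, gives each scale its own repeated measures ANOVA, in which "an interaction term between treatment group and time will be included to examine treatment group-related differences in the assessments for each outcome". Then: "Each significant interaction will be followed up with paired t-tests to examine treatment differences at each set of time points".

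The same section treats multiplicity in two branches.

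- **First branch.** "we do not plan formal multiple comparison adjustments if the results fit a coherent pattern that is consistent" with similar studies. The reason given is that "each result will reinforce the other, rather than detracting from one another, as required by formal multiple comparisons adjustments such as Bonferroni".
- **Second branch.** "if only one or a very few measures reach statistical significance and their directions and/or magnitudes do not coherently fit" with prior expectations, the report will note that results below .05 "lack plausibility and could be due to chance, despite meeting the conventional cutoff for statistical significance".

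Under Missing Data, every analysis is run twice, "performing analysis with 2 versions of scores", and neither version is named as the deciding one.

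**The concern.** The opening condition of the first branch suggests that some adjustment follows when it fails. The second branch supplies only a sentence in the report. Each outcome is therefore read at .05 whichever branch applies.

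The branch is chosen once the results are known. Neither document defines coherence, says how many outcomes count as very few, states the expected magnitudes, or names the similar studies. Favourable directions can be inferred from the scale descriptions, but the rest is left to judgement.

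The weak spot is a single significant result in the favourable direction. The second branch requires poor fit with expectations, which such a result may not show. The first branch argues from several results supporting one another, which is awkward for a lone result. Two analysts could report the same p-value as a finding or as possibly chance, and this is the situation in which multiplicity matters most.

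**Working it through.** **1. The plan's own figure.** SAP, Design, states .80 power for a medium effect with N = 400 at p = .05; randomisation is 3:1, so 300 and 100. No number is given for medium. Assuming d = .5, a two-sided two-sample test has power .991. Power of .80 corresponds to d = (1.960 + 0.842) × √(1/300 + 1/100) = 2.802 × 0.1155 = 0.32. The .80 is not reproduced with d = .5, so both effect sizes are carried through below.

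**2. Familywise error with no effect on any outcome.** Inputs from the SAP: four outcomes, three time points (so a 2-df interaction), threshold .05. Correlations between outcomes are not in the documents; 0 to .8 are assumed, equal for all pairs.

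At correlation 0: 1 − 0.95⁴ = .1855. For other values, simulate for each outcome A² + B², where A is the standardised group difference in change from baseline to month 6 and B is the orthogonal contrast. Compare with the chi-square (2 df) cutoff: 5.99 at .05, and 8.76 at .05/4 = .0125. Favourable means A > 0, which is an assumption about how direction would be read.

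| Event, % of null trials | r = 0 | .3 | .5 | .7 | .8 |
|---|---|---|---|---|---|
| Any significant, either direction | 18.5 | 17.5 | 15.8 | 13.3 | 11.7 |
| Any significant and favourable | 9.6 | 9.0 | 8.1 | 6.9 | 6.1 |
| Exactly one significant, and favourable | 8.6 | 7.7 | 6.3 | 4.4 | 3.4 |
| – of these, all four outcomes point favourably | 1.1 | 2.9 | 3.6 | 3.4 | 2.8 |
| At least two significant and favourable | 0.4 | 0.9 | 1.5 | 2.1 | 2.4 |
| Holm, any significant | 4.9 | 4.7 | 4.4 | 3.8 | 3.3 |

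Ratios: 18.5/5 = 3.7 and 11.7/5 = 2.3 in either direction; 9.6/2.5 = 3.8 and 6.1/2.5 = 2.4 for a favourable result. The Holm row uses the .0125 first step, which alone determines Holm's familywise error when all four nulls are true.

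**3. Power cost of Holm at its first step (.05 to .0125).**

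- Two-sample, 300/100: d = .5, from .99 to .965; d = .32, from .80 to about .62.
- Planned interaction, assuming group differences of 0, .25 and .50 SD at the three visits. Noncentrality = (300 × 100/400) × (.0625 + 0 + .0625)/(1 − ρ) = 9.375/(1 − ρ), where ρ is the within-person correlation, with 2 and 796 df.
- With an assumed 30% dropout (210/70) this becomes 52.5 × .125/(1 − ρ) = 6.56/(1 − ρ), with 2 and 556 df.

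| ρ | 300/100: .05 → .0125 | 210/70: .05 → .0125 |
|---|---|---|
| .3 | .915 → .80 | .79 → .60 |
| .5 | .98 → .93 | .91 → .79 |
| .7 | .999 → .997 | .99 → .97 |

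**The case against.** **The SAP declines adjustment openly and gives a reason.** This stands. A reader might infer that a promised 5% familywise rate is broken; the SAP makes no such promise.

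**A lone favourable result is not plainly outside both branches.** This also stands. The first branch speaks of the results, not only the significant ones, so one significant outcome with the other three also pointing favourably can be read as coherent. That covers 1.1 to 3.6 percentage points of the null trials with a lone favourable result. The second branch also mentions magnitudes, so a favourable result of implausible size may be caught there. The text supports a charge of ambiguity, not of a case that is certainly unclassified.

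**The 18.5 to 11.7% counts both directions and applies only if any result is claimed.** Correct. About half of those trials have no favourable significant result, and the second branch would flag many of them. The absolute figure for a favourable claim is therefore 9.6 to 6.1%, but the ratio to its 2.5% benchmark is much the same.

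**A coherence rule can protect.** It can, if it means at least two significant favourable results. The SAP does not say that it does.

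**The ambiguous case may simply reflect one real effect.** If only one effect is real, a lone favourable result would be common and nearly always true. Its frequency shows that the rule would often need interpreting; it is not a measure of error.

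**The follow-up t-tests are gated.** The gate works within an outcome and does nothing across the four.

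**Conclusion.** The concern holds in this form: the multiplicity rule is applied after the results, turns on an undefined criterion, changes no threshold in either branch, and is ambiguous for a lone significant favourable result. If any one unadjusted result may be claimed, familywise error is roughly two to almost four times nominal. If coherence were defined as two or more significant favourable results, there would be no inflation. A single error rate for the plan therefore cannot be given.

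The figures rest on assumed equal correlations between outcomes (0 to .8), large-sample 2-df tests, and direction read from the change between baseline and month 6. This is a change that should be made; it is not a fatal flaw.

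**What to change.** Prespecify Holm at an overall two-sided .05 across the four group by time interactions. Let it decide which outcomes are claimed and which go on to the follow-up t-tests. Name the missing-data version that Holm uses. Keep the coherence paragraph as interpretation only. Holm would then control error for the interactions; it would not cover the follow-up t-tests or the second missing-data version, and the SAP should say so.

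Outcomes, tests and data collection do not change, but the power statement must say which alpha it refers to.

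The price is power per outcome at the first step. It is small at d = .5 with full data, provided the within-person correlation is about .5 or more. It is larger at lower correlation or with dropout, and largest if .80 is the true starting point. Later Holm steps are less strict: if all four effects are real at that size, average power per outcome is .70 to .73; if only one is real, about .63.

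A named single primary or a ranked sequence would also settle the matter. If the sponsor keeps unadjusted tests, the minimum is to state that familywise error is not controlled, define coherence before results are seen, and say how a lone favourable result will be reported. That costs no power.
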